1. Subjects in the **Treatment Continuation Cohort** will remain on their current dosage of pexidartinib and undergo study assessments at 3-month intervals for a maximum of 24 months.
2. Subjects from the **Treatment-Free/Re-Treatment Cohort** who enter the Treatment-Free period will undergo study assessments 1 month after enrollment, 3 months after enrollment, and then at 3-month intervals for 24 months or until re-treatment with pexidartinib.

Subjects from the **Treatment-Free/Re-Treatment Cohort** who enter the Re-Treatment period will undergo efficacy and safety study assessments at 3-month intervals until the total time within this Cohort reaches 24 months; a new Baseline will be established upon entry into re-treatment. Liver safety assessments will follow a separate schedule.

All subjects will remain on study for a maximum of 24 months. The study will end with the completion of the last subject's 30-day safety follow-up or with their withdrawal from the study. A post-trial access plan, delineating options for access to pexidartinib, will be available for subjects after completing their study participation if the subject is benefiting from the study drug.

Key Eligibility Criteria

Subjects must meet the following key inclusion/exclusion criteria:

Inclusion Criteria:

1. Currently enrolled and have not discontinued pexidartinib treatment in one of the following studies: Study PLX108-10 (ENLIVEN), Study PLX108-01, Study PL3397-A-A103, or Study PL3397-A-U126.
2. Willing and able to complete the PROMIS Physical Function Scale and EQ-5D-5L throughout the study.
3. Willing and able to provide written informed consent prior to any study-related procedures and to comply with all study requirements.
4. Females of reproductive potential must have a negative urine pregnancy test at Screening/Baseline (to be confirmed by a serum pregnancy test taken on the last-treatment visit of their prior study) and should be advised to use an effective,

non-hormonal method of contraception during treatment with pexidartinib and for 1 month after the last dose. Males with female partners of reproductive potential should be advised to use an effective method of contraception during treatment with pexidartinib and for 1 month after the last dose. Female partners of male patients should concurrently use effective contraceptive methods (hormonal or non-hormonal).

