3. OBJECTIVES, OUTCOME MEASURES, AND ENDPOINTS

The objectives, definitions of associated endpoints, as well as applicable outcome measures are described in [Table 3.1](#) and [Table 3.2](#). Further requirements for the endpoint analyses and censoring rules, where applicable, can be found in [Section 9.5.1](#), [Section 9.5.2](#), and [Section 9.5.3](#).

Table 3.1: Description of Objectives, Outcome Measures, and Endpoints (Treatment-Free/Re-Treatment Cohort)

Period	Objectives	Outcome Measure	Endpoints	Category
Primary Objective				
Overall	Proportion of subjects who remain treatment-free	
Title: Proportion of treatment-free subjects at 12 months and 24 months
 
Description: Proportion of subjects who remain treatment-free at Month 12 and Month 24
 
Time frame: 24 months after last subject enrolled in the Cohort
	Proportion of subjects who remain treatment-free at Month 12 and Month 24	Efficacy
Secondary Objectives				
Treatment-Free period	Change from Baseline in Patient Reported Outcomes (PROs)	
Title: Change from Baseline in PROs
 
Description: Change from Baseline in PROs (PROMIS PF, EQ-5D-5L)
 
Time frame: 24 months after last subject enrolled in the Cohort
	Mean change from Baseline* for PROMIS PF and EQ-5D-5L quarterly for the treatment-free and Re-Treatment periods. *Note: Baseline is Screening values.	Efficacy
	Safety	
Title: Number of subjects with AE during the Treatment-Free period*
 
Description: Total number of subjects in the safety analysis set with any AE collected between Screening and start of re-treatment or final database lock (whichever occurs first)
 
Time frame: 24 months after last subject enrolled in the Cohort
 
*Note: Listed as a secondary objective but is a primary outcome measure.
	Incidence of AEs and SAEs, ECGs, and laboratory assessments	Safety
Re-Treatment period	Tumor Assessment	
Title: Tumor assessment
 
Description: Investigator evaluation of tumor
 
Time frame: 24 months after last subject enrolled in the Cohort
	Qualitative assessment of the tumor	Efficacy

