	Change from Baseline in Patient Reported Outcomes (PROs)	
Title: Change from Baseline in PROs
 
Description: Change from Baseline in PROs (PROMIS PF, EQ-5D-5L)
 
Time frame: 24 months after last subject enrolled in the Cohort
	Mean change from Baseline* for PROMIS PF and EQ-5D-5L quarterly for the Re-Treatment periods. *Note: Baseline is reinitiated with subject entering Re-Treatment period.	Efficacy
	Safety	
Title: Number of subjects with AE during the Re-Treatment period*
	Incidence of TEAEs and SAEs, ECGs, and laboratory assessments	Safety

Period	Objectives	Outcome Measure	Endpoints	Category
		
Description: Total number of subjects in the safety analysis set with any AE collected between first re-treatment dose and final database lock
 
Time frame: 24 months after last subject enrolled in the Cohort
 
*Note: Listed as a secondary objective but is a primary outcome measure.
		

AE = adverse event; EQ-5D-5L = EuroQol-Five Dimension Five Level Scale; PRO = Patient-Reported Outcomes ; PROMIS PF = Patient-Reported Outcomes Measurement Information System – Physical Function; SAE = serious adverse event; TEAE = treatment-emergent adverse event

Table 3.2: Description of Objectives, Outcome Measures, and Endpoints (Treatment Continuation Cohort)

Objectives	Outcome Measure	Endpoints	Category
Primary Objective			
None			
Secondary Objectives			
Tumor Assessment	
Title: Tumor assessment
 
Description: Investigator evaluation of tumor
 
Time frame: 24 months after last subject enrolled in the Cohort
	Qualitative assessment of the tumor	Efficacy
Change from Baseline in PROs	
Title: Change from Baseline in PROs
 
Description: Change from Baseline in PROs (PROMIS PF, EQ-5D-5L)
 
Time frame: 24 months after last subject enrolled in the Cohort
	Mean change from Baseline* for PROMIS PF and EQ-5D-5L at quarterly assessments. 
*Note: Baseline is Screening values.
	Efficacy
Safety	
Title: Number of subjects with TEAE during the study*
 
Description: Total number of subjects in the safety analysis set with any AE collected between first dose and final database lock
 
Time frame: 24 months after last subject enrolled in the Cohort
 
*Note: Listed as a secondary objective but is a primary outcome measure.
	Incidence of TEAEs and SAEs, ECGs, and laboratory assessments	Safety

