9.5.2. Safety Analyses

Safety analyses will be performed using the Safety Analysis Set and subjects will be analyzed by cohort separately.

Adverse Events

TEAEs are defined as new AEs or pre-existing conditions that worsen in CTCAE grade after the first dose of study drug and up to 30 days after last dose of study drug. AEs collected after 30 days after the last dose of study drug will not be considered TEAEs unless they are treatment related. AEs will be coded using the Medical Dictionary for Regulatory Activities (MedDRA) dictionary. An AE will be assigned to the study period in which it started, even if it resolved in a subsequent period. Incidence of TEAEs occurring over time, (e.g., 0 to 6 months, 6 to 12 months, etc.) will be summarized. The number and percentage of subjects reporting TEAEs will be calculated overall, by system organ class, by preferred term, and by cohort.

TEAEs will be further summarized by CTCAE grade and relationship to study drug. Similarly, the number and percentage of subjects reporting treatment-emergent SAEs and related treatment-emergent SAEs will be tabulated, and TEAEs leading to discontinuation of study drug.

A by-subject AE (including treatment-emergent) data listing including but not limited to verbatim term, preferred term, system organ class, CTCAE grade, and relationship to study drug will be provided. Deaths, other SAEs, AESIs, and AEs associated with study drug discontinuation, will be listed. AEs due to COVID-19 will be also summarized and listed.

Clinical Laboratory Evaluation

Descriptive statistics will be provided for the clinical laboratory results by scheduled time of evaluation and by cohort, as well as for the change from Baseline. The Baseline value is defined as the last non-missing value before the initial administration of study drug. In addition, mean change from Baseline will be presented for the maximum and minimum post-treatment values and the values at the EOT visit.

Abnormal clinical laboratory results will be graded according to NCI-CTCAE version 5.0, if applicable, and the grade will be presented in a by-subject data listing. A shift table, presenting by cohort the two-way frequency tabulation for baseline and the worst post-treatment value according to the CTCAE grade, will be provided for clinical laboratory tests. A listing of abnormal clinical laboratory test results deemed of clinical significance or of Grade 3 or 4 will be generated.

ECG

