Descriptive statistics will be provided for the ECG measurements by scheduled time of evaluation and by cohort, as well as for the change from Baseline. The Baseline value is defined as the last non-missing value before the initial administration of study treatment. A listing of ECG data will be generated.

Vital Signs

Descriptive statistics will be provided for the vital sign measurements by scheduled time of evaluation and by cohort, as well as for the change from Baseline. The Baseline value is defined as the last non-missing value before the initial administration of study treatment. A listing of vital sign data will be generated.

Other

Listings of all other safety endpoints (e.g., physical examination findings) will be generated.

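### Section 9.5.2 does not split laboratory and vital-sign summaries by period in the Treatment-Free/Re-Treatment Cohort, so off-drug and re-treatment values can share a row

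*Combined protocol and SAP*

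**What the plan says.** Section 9.5.2 sets the frame: "Safety analyses will be performed using the Safety Analysis Set and subjects will be analyzed by cohort separately". For laboratory data it continues: "Descriptive statistics will be provided for the clinical laboratory results by scheduled time of evaluation and by cohort", with change from Baseline handled the same way. Vital signs have a parallel sentence: "Descriptive statistics will be provided for the vital sign measurements by scheduled time of evaluation and by cohort". The laboratory shift table of Baseline against worst CTCAE grade is also by cohort, and the changes to maximum and minimum values have no period split. The section does contain a period rule, but only for adverse events: "An AE will be assigned to the study period in which it started, even if it resolved in a subsequent period".

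Section 9.4 analyses subjects in two cohorts. Treatment-Free and Re-Treatment are periods inside one of them. Section 9.4 also defines a Re-Treatment Analysis Set (RAS) and gives it both efficacy and safety uses.

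Table 3.1 sets the safety endpoints by period. Off drug the endpoint is "Incidence of AEs and SAEs, ECGs, and laboratory assessments"; on re-treatment it is "Incidence of TEAEs and SAEs, ECGs, and laboratory assessments". On restarting, the synopsis says, "a new Baseline will be established upon entry into re-treatment".

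**The concern.** The study exists to describe what happens when pexidartinib is stopped and when it is restarted. If one row of a laboratory or vital-sign table can hold both off-drug and re-treatment values, it describes neither state, and the period-specific laboratory endpoints of Table 3.1 have no by-visit summary that delivers them. A subject may also enter the same row twice, and no rule says which record counts.

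**Working it through.** The plan gives no figure to reproduce. The check compares the two visit schedules.

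**1. Clocks.** Table 1.2 visits are counted from enrollment (Sections 4.1.1 and 4.1.4). Table 1.3 starts at BL-2. A month is 30 days, except 28 days for M1/M2 in Table 1.3. Total time in the cohort is capped at 24 months (Section 4.1.4; Table 1.3, footnote b).

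**2. Shared labels after baseline.**

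| Assessment | Table 1.2 (off drug) | Table 1.3 (re-treatment) | Shared among M1, M3, M6, M9 |
|---|---|---|---|
| Vital signs | M1, M3/M15, M6/M18, M9/M21, M12, M24 | M1/M2, M3, M6, M9, Mx | M1, M3, M6, M9 |
| Hematology, chemistry, coagulation, liver tests | M6/M18, M12, M24 | M1/M2, M3, M6, M9, Mx | M6 |
| Urinalysis | M6/M18, M12, M24 | M1/M2, M6, Mx, EOT | M6 |
| ECG | M24 | EOT | none |

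The synopsis instead puts chemistry and hematology at 3-month intervals. If that governs, M3 and M9 are shared as well, but still not M1.

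**3. Two values from one subject.** Let R be the month of restart. An off-drug value at month m needs R ≥ m. A re-treatment value at month m needs R + m ≤ 24. Both exist when m ≤ R ≤ 24 − m:

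- M1: 1 ≤ R ≤ 23
- M3: 3 ≤ R ≤ 21
- M6: 6 ≤ R ≤ 18
- M9: 9 ≤ R ≤ 15
- M12: R = 12 only, an edge case
- M18: would need 18 ≤ R ≤ 6, so impossible

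These limits ignore visit windows and are approximate. Example: with R = 9, the off-drug M6 falls on day 6 × 30 = 180 and the re-treatment M6 on study day (9 + 6) × 30 = 450.

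**4. Later visits.** If Mx is counted from BL-2, laboratory labels M12 and M18 could mix different subjects (restart by month 24 − 12 = 12 and by month 24 − 18 = 6). The clock for Mx is unclear. Footnote b refers to visits up to 21 months after baseline, and the urinalysis comment names M24, which a subject who restarts after enrollment cannot reach from BL-2 under the cap. Later overlap is therefore possible, not established.

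**5. Tables without visit labels.** The shift table takes one worst value per subject. Taken over all follow-up in this study, a restarter's worst value may come from either period and the table does not show which. The same applies to the maximum and minimum. If post-treatment is instead read as after the first in-study dose, off-drug values drop out and the Treatment-Free period has no such table.

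**6. Baseline.** Section 9.5.2 ties Baseline to the first administration of study drug. On the in-study reading, a restarter's off-drug M6 precedes its own Baseline, and a subject who never restarts has no such dose. The synopsis makes the prior-study End-of-Treatment assessments the entry Baseline and sets a new one at re-treatment. Section 9.5.1.2 carries that reset into the RAS analysis of patient-reported outcomes; Section 9.5.2 does not carry it into laboratory data or vital signs.

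**The case against.** The strongest reply is that pooling is nowhere stated. The text refers to scheduled time, not visit name; each period has its own schedule, and month 6 after enrollment and month 6 after BL-2 can be read as different times. Table 3.1 and the RAS both signal a split, Section 9.5 calls itself a summary, and analysis-visit rules may sit in a SAP. The study is descriptive, without p-values, and graded listings by subject are planned.

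Much of this stands. Mixing is what a literal reading permits, not a declared intention. It does not remove the gap: Section 9.5.2 never invokes the RAS, provides no off-drug-only table, and splits by period only for adverse events. The document supplied contains no SAP text that settles the matter.

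Two stronger readings are tempting and fail. A reader might infer that laboratory rows collide at all four shared labels; under Table 1.2 there are no laboratory tests at M1, M3 or M9. A reader might also infer that pooling would hide the aminotransferase rise that Section 2.1.2 places mainly in the first 8 weeks of treatment. Re-treatment tests in that window are weekly and at M1/M2. Table 1.2 has no liver tests at M1 and no M2 visit, so those values have no off-drug row to be averaged with. The M6 collision falls about four months later (180 − 56 = 124 days), and the documents give no basis for the size of a change there.

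**Conclusion.** The concern holds in limited form. As written, the by-cohort rule does not deliver the laboratory endpoints that Table 3.1 sets for each period, and it can mix off-drug and re-treatment values. For vital signs, which Table 3.1 does not name as an endpoint, the shared labels are M1, M3, M6 and M9. For laboratory tests under Table 1.2 the established overlap is M6, with two values from any subject restarting between about Month 6 and Month 18. M3 and M9 are added for chemistry and hematology under the synopsis schedule. The laboratory shift and maximum/minimum summaries are also unsplit.

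How many subjects would be affected, and whether opposite changes would cancel, cannot be sized: the documents give neither restart rates nor expected changes. The result rests on the nominal schedule, the 24-month cap and re-treatment visits counted from BL-2. The primary treatment-free analysis is not affected. The point is worth correcting because the remedy is small.

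**What to change.** In Section 9.5.2, require laboratory results (including the shift and maximum/minimum tables) and vital signs to be summarised by period within the Treatment-Free/Re-Treatment Cohort, and by scheduled time within period:

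- **Treatment-Free:** visits counted from enrollment and ending before the first re-treatment dose, with the prior-study End-of-Treatment values as Baseline.
- **Re-Treatment:** subjects in the RAS, visits counted from BL-2, with BL-2 as Baseline.

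Use these Baselines for this cohort in place of the single first-dose definition. ECG may follow the same split for consistency, although its scheduled visits do not collide. The synopsis 3-month laboratory schedule and Table 1.2 must be reconciled.

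The cost is a short text change and one further split of the tables. No new data are needed. The downside is smaller numbers per row.

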1.3. Schedule of Events

Table 1.1: Schedule of Events: Treatment Continuation Cohort

	Visits	SCR	BL	M3	M6	M9	M12	M15	M18	M21	EOT ^a	EOS/AE F/U ^b	Comment
	Window (Days)	0*	0*	±7	±7	±7	±14	±14	±14	±14	±7	±7	* SCR and BL will both occur on EOT visit of preceding study.
Assessments	Procedure												
Informed consent		X											Obtain prior to performing any study procedures
Eligibility assessment			X ^c										
Demographics/Medical history/Prior medications, non-drug therapies, and radiotherapy/Height	N/A												This information will be transferred from prior studies
Vitals	Vital signs and weight	X	X ^c	X	X	X	X	X	X	X	X		
PRO instruments	EQ-5D-5L		X ^c	X	X	X	X	X	X	X	X		Performed before any physical tests
	PROMIS PF		X ^c	X	X	X	X	X	X	X	X		Physical Function Scale performed before any physical tests
Safety	Physical exam	X	X ^c	X	X	X	X	X	X	X	X		Full PE on Screening and EOS, abbreviated PE at other visits. All PE exams will include functional assessment for the affected joint.
	ECG	X	X ^c								X		May be performed whenever deemed medically necessary and at any visit during which a subject exhibits a heart rate ≤50 bpm. Any abnormal finding should be confirmed with a repeated ECG. ECGs should be performed after vital signs assessments.

	Visits	SCR	BL	M3	M6	M9	M12	M15	M18	M21	EOT ^a	EOS/AE F/U ^b	Comment
	Window (Days)	0*	0*	±7	±7	±7	±14	±14	±14	±14	±7	±7	* SCR and BL will both occur on EOT visit of preceding study.
Assessments	Procedure												
AE	TEAE/SAE		X ^c					X			X		See Section 8.4.1
Concomitant medications, non-drug therapies, and radiotherapy	Concomitant		X ^c					X					
Laboratory assessments	Hematology		X ^c	X	X	X	X	X	X	X			See Section 10.2 for details
	Chemistry		X ^c	X	X	X	X	X	X	X			See Section 10.2 for details
	Urinalysis		X ^c		X		X		X		X		See Section 10.2 for details
	Coagulation		X ^c	X	X	X	X	X	X	X	X		See Section 10.2 for details
	Serum pregnancy test	X	X ^d								X		For females of reproductive potential (as defined in Section 5.1)
	Liver function tests		X	X	X	X	X	X	X	X	X		AST, ALT, ALP, total bilirubin, GGT, direct bilirubin
	Hormone testing		X ^c										Females only, FSH to confirm postmenopausal status
	TSH	X	X										
Treatment response/Disease assessment	MRI of affected joint		X ^c		X		X		X		X ^e		Tumor assessment. Additional imaging assessments may be performed with changes in tumor response(s), as deemed necessary by the Investigator.

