Note: In case of early discontinuation from the study, subjects must complete all the assessments corresponding to the M24 visit.

^a Subjects are allowed to continue past 12 months within the Treatment-Free period and will follow quarterly visits as per the 12-month visit until they enter the Re-Treatment period or the EOS, whereupon they will complete the EOS Visit and 30-day safety follow-up.

^b The End-of-Study will be reached with a follow-up phone call 1-month post-last study visit to collect AE information.

^c Assessment does not need to be repeated if the procedure was done at End-of-Treatment visit of preceding study.

Table 1.3: Schedule of Events: Re-Treatment Period^a of Treatment-Free/Re-Treatment Cohort

	Visits	BL-2	M1, M2 (LFT) ^a	M3	M6	M9	Mx ^b	EOT ^c	EOS/ AE FU ^d	Comment
	Window (Days)	0	±3	±3	±14	±14	±14	±7		
Assessments	Procedure									
Vitals	Vital signs and weight	X	X	X	X	X	X			
PRO instruments	EQ-5D-5L	X		X	X	X	X			Performed before any physical tests
	PROMIS PF	X		X	X	X	X			Physical Function Scale performed before any physical tests
Safety	Physical exam	X	X	X	X	X	X			Full PE on EOS, abbreviated PE at first re-treatment and at other visits. All PEs will include functional assessment for the affected joint
	ECG	X						X		May be performed whenever deemed medically necessary and at any visit during which a subject exhibits a heart rate ≤50 bpm. Any abnormal finding should be confirmed with a repeated ECG. ECGs should be performed after vital signs assessments.
AE	TEAE/SAE							X		
Concomitant medications, non-drug therapies, and radiotherapy	Concomitant					X				
Laboratory assessments	Hematology	X	X	X	X	X	X			See Section 10.2 for details
	Chemistry	X	X	X	X	X	X			See Section 10.2 for details
	Urinalysis	X	X		X		X	X		See Section 10.2 for details. Only perform every 6 months (ie, M12, M18, and M24)
	Coagulation	X	X	X	X	X	X			See Section 10.2 for details
	Serum pregnancy test	X	X	X	X	X	X	X		For females of reproductive potential (as defined in Section 5.1)
	Liver function tests ^a	X	X ^a	X	X	X	X	X		

	Visits	BL-2	M1, M2 (LFT) ^a	M3	M6	M9	Mx ^b	EOT ^c	EOS/AE FU ^d	Comment
	Window (Days)	0	±3	±3	±14	±14	±14	±7		
Assessments	Procedure									
	Hormone testing	X								Females only, FSH to confirm postmenopausal status
	TSH	X								

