Treatment Response/ Disease Assessment	MRI of affected joint	X ^e		X	X	X	X	X ^f		Tumor assessment. Additional imaging assessments may be performed with changes in tumor response(s) as deemed necessary by the Investigator.
Dosing Diary	Provide Diary		X	X	X	X	X			Diary for pill count and AEs between scheduled clinic visits
	Review Diary			X	X	X	X	X		
	Dispense 3-month supply	X		X	X	X	X			A drug supply for more than 3 months may be dispensed.
Study Drug: Pexidartinib	Collect Returned/ Assess Treatment Compliance			X	X	X	X	X		
EOS Form									X	

AE = adverse event; BL = baseline; D = day; ECG = electrocardiogram; EOS = End of Study; EOT = End-of-Treatment; EQ-5D-5L = European Quality of Life Five Dimension Five Level Scale; FSH = follicle stimulating hormone; FU = Follow-up; M = month; MRI = magnetic resonance imaging; PRO = Patient-Reported Outcome; PROMIS PF = Patient-Reported Outcomes Measurement Information System – Physical Function; SAE = serious adverse events; SCR = screening; TEAE = treatment emergent adverse events; TVS = tumor volume score.

Note: For all visits, a month is considered a 30-day interval, except for the M1/M2 visit for re-treatment patients where there is a 28-day window.

^a Pexidartinib will be administered at the dose at which subject completed the prior study. Doses will be taken on an empty stomach (at least 1 hour before or 2 hours after a meal or snack), at approximately the same times of the day, and approximately 12 hours apart. Weekly liver monitoring tests for the first 8 weeks, then every 2 weeks for 1 month, then every 3 months or more frequently as directed by the Investigator.

^b Patient visits should be done every 3 Months until 21 Months after baseline. The combined overall study duration of all treatment, treatment-free, and re-treatment phases should not exceed 24 months.

^c The EOT visit should occur within 7 days after the last dose of pexidartinib or at the time the decision is made to discontinue pexidartinib (if this is more than 7 days after the last dose of pexidartinib), unless there is a medical condition that prevents subjects from completing the visit within this time.

^d The End-of-Study will be reached with a follow-up phone call 1-month post-EOT visit to collect AE information.

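### Section 9.5.2 plans laboratory changes at the EOT visit, but Tables 1.1 and 1.3 mark no hematology or chemistry panel there, and Table 1.3 marks no PRO at EOT

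*Combined protocol and SAP*

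**What the plan says.** **Analysis.** Section 9.5.2 (Clinical Laboratory Evaluation) plans descriptive statistics by scheduled time, a CTCAE shift table to the worst post-treatment value, and also that "mean change from Baseline will be presented for the maximum and minimum post-treatment values and the values at the EOT visit". No panel is named.

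**Schedule, Treatment Continuation (Table 1.1).** Two laboratory rows end at M21: "Hematology X ^c X X X X X X X See Section 10.2 for details" and "Chemistry X ^c X X X X X X X See Section 10.2 for details". The coagulation row carries one mark more, at EOT: "Coagulation X ^c X X X X X X X X See Section 10.2 for details". The liver function row, defined as "AST, ALT, ALP, total bilirubin, GGT, direct bilirubin", is also marked at EOT, as are urinalysis and both PRO instruments.

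**Schedule, Re-Treatment (Table 1.3).** Hematology, chemistry, coagulation, EQ-5D-5L and PROMIS PF all stop at the Mx column. Liver function tests, urinalysis and the serum pregnancy test are marked at EOT. Footnote b, attached to Mx, says: "Patient visits should be done every 3 Months until 21 Months after baseline". The physical examination comment reads "Full PE on EOS, abbreviated PE at first re-treatment and at other visits", while footnote d makes EOS a "follow-up phone call 1-month post-EOT visit to collect AE information".

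**Body text.** The synopsis (Study Design) and Section 4.1.1 call for PROs every 3 months in all subjects. The synopsis gives the same frequency for chemistry and hematology. Section 7.1 refers the reader to the Schedule of Events for what is collected at discontinuation.

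**The concern.** An analysis planned for a named visit needs the data to be scheduled at that visit. Because Section 7.1 defers to the tables, a site following them would draw no hematology and no full chemistry panel at EOT, and the statistician would have nothing to summarize there beyond the panels that are marked.

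The PRO gap is a separate matter. It does not conflict with the laboratory sentence in Section 9.5.2. It conflicts with the 3-monthly PRO requirement and departs from Table 1.1. Change in PROs during re-treatment is a secondary endpoint (Table 3.1), analyzed in the Re-Treatment Analysis Set (Section 9.5.1.2). That set includes everyone with at least one re-treatment dose, yet a subject who stops early may contribute little or nothing to it. The contrast with Table 1.2 is notable: a subject leaving the Treatment-Free period early must complete the M24 assessments, which include hematology, chemistry and both PROs.

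**Working it through.** The plan gives no figure to reproduce, so the check sets the schedule against the analysis and counts analytes.

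**Step 1. EOT cell, row by row.**

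| Row | Table 1.1 EOT | Table 1.3 EOT |
|---|---|---|
| Hematology | empty | empty |
| Chemistry | empty | empty |
| Coagulation | marked | empty |
| Liver function tests | marked | marked |
| Urinalysis | marked | marked |
| EQ-5D-5L | marked | empty |
| PROMIS PF | marked | empty |

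Each of these rows has its full number of visit cells (11 in Table 1.1, 8 in Table 1.3), so the empty cells do not come from a shifted row.

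**Step 2. What is missing from the EOT laboratory summary.** Table 10.1 lists 27 blood chemistry analytes (13 in its first column, 14 in its second, counting the optional albumin/globulin ratio and the calculated creatinine clearance). Six of them (AST, ALT, ALP, GGT, total and direct bilirubin) reach EOT through the liver function row. Table 1.3 does not list the analytes of that row, but Section 2.3 names the same six for monitoring after restart.

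- Chemistry without an EOT value: 27 − 6 = 21 of 27.
- Hematology without an EOT value: all 10 parameters (5 counts and indices, 5 differential).
- Coagulation: available in Table 1.1, not in Table 1.3.

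**Step 3. Early stopping in Re-Treatment.** Table 1.3 marks PROs at BL-2, M3, M6, M9 and Mx, and not at M1/M2. After EOT only the telephone contact remains, apart from an MRI in some subjects. A subject who stops between two quarterly visits therefore has no PRO at the end of treatment. One who stops before M3 has none after restart, so no change from BL-2 can be computed.

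**Step 4. Subjects who stay to month 24.** For a restart at study month m, month 24 falls 24 − m months after BL-2.

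- m = 15, 18 or 21 gives 9, 6 or 3. These are the M9, M6 and M3 columns, which mark PROs and do not carry footnote b. Nothing is lost.
- m = 3, 6, 9 or 12 gives 21, 18, 15 or 12. These fall under Mx, so the answer depends on the baseline that footnote b means. If it is BL-2, all four are within 21 months and the PRO is marked. If it is study baseline, the last Mx visit is study month 21, and month 24 has only an EOT visit without PROs.

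Footnote b does not say which baseline applies, and the synopsis (Study Duration) establishes a new one at restart. No percentage loss can therefore be stated.

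**The case against.** The best defense has four parts.

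1. **The safety-critical analytes are covered.** This stands. The six liver analytes, which bear directly on the hepatotoxicity of special interest in Section 8.4.1.2, are scheduled at EOT in both tables. A reader might infer that the whole EOT laboratory summary is impossible; it is not. The gap is hematology, non-liver chemistry and, in Table 1.3, coagulation. The maximum, minimum, by-visit and shift summaries can still be produced.

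2. **The body text already requires 3-monthly assessments to month 24.** This stands in part. It makes the empty PRO cells a conflict between text and table, but a 3-monthly frequency does not supply an assessment at an EOT visit that falls between quarters.

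3. **The PRO endpoint is quarterly, and no analysis uses an EOT PRO.** This is fair. An EOT questionnaire would not enter the quarterly means without a rule for assigning it to a visit, so the fix needs that rule. It also means that selection bias in those means, which a reader might infer, is not demonstrated: Section 7.1 lists complete response as well as adverse events and progression among reasons for leaving, and an EOT PRO would not fill later quarters.

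4. **The marks may not be reliable.** In the text of the PDF, the adverse event and concomitant medication rows of Table 1.3 each show a single mark that looks like a merged span. Full cell counts and marked neighboring rows make lost marks unlikely in the rows at issue, but do not exclude them.

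**Conclusion.** The inconsistency holds within limits. As written, the EOT laboratory summary lacks hematology and 21 of 27 chemistry analytes in both on-treatment schedules, and coagulation in Table 1.3. Re-treated subjects who stop early have no end-of-treatment PRO, and those who stop before M3 have no post-restart PRO.

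A reader might go further and infer that every re-treated subject loses the month-24 PRO, or that a fixed share of quarterly PROs is lost. The documents do not support this: late restarters have a marked visit at month 24, and for earlier ones the answer turns on an undefined baseline.

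The study is descriptive, without p-values (Section 9.1), and the primary endpoint is unaffected. The protocol gives neither a sample size nor an expected number of restarts, so the number of subjects concerned is unknown. The conclusion assumes that the EOT marks are as read and that the tables govern collection at discontinuation, as Section 7.1 indicates. The point should be corrected, but it does not threaten the study's main result.

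**What to change.** - **PROs.** Mark EQ-5D-5L and PROMIS PF at EOT in Table 1.3, as in Table 1.1. State in the SAP how an EOT PRO is assigned to a quarterly visit, and say which baseline footnote b means.
- **Laboratory rows.** Reconcile the EOT cells of Tables 1.1 and 1.3 with Section 9.5.2: either the values are collected at EOT, or Section 9.5.2 uses the last on-treatment value. Which of the two is for the sponsor to decide.
- **Examination.** Reconcile the Table 1.3 comment placing the full examination at EOS with the telephone contact in footnote d. Neither EOT nor EOS carries an examination mark in that table.
- **Check.** Compare the EOT marks with the original PDF before amending.

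The cost is table and SAP wording, plus a little subject time for two questionnaires at a visit that already takes place. If the sponsor chooses to collect the laboratory values, those panels are added to a visit at which blood is already drawn for liver tests.
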